9.1. Intervention description

The on-treatment biopsy consists of a tissue sampling performed during the ongoing systemic therapy, after one cycle of neoadjuvant therapy. The procedure will be carried out under local anesthesia by experienced clinicians, using standard sterile techniques and imaging guidance if required (e.g., ultrasound). No comparator, placebo, or sham procedure is foreseen. The study is non-randomized and all patients continue to receive standard-of-care therapy as per clinical indications.

9.2. Treatment Schedule

Patients will receive standard-of-care neoadjuvant chemotherapy according to sequential anthracycline and taxane regimens as per standard guidelines. In addition, patients with triple-negative breast cancer (TNBC) will receive immunotherapy with pembrolizumab as per clinical practice (as the KEYNOTE-522 schema).

9.3. Method for Assigning Subjects to Treatment/Intervention Groups

Not applicable

9.4. Blinding of treatment/procedure

Not applicable

9.5. Preparation, Administration and Accountability of the study Treatments

This study does not include the administration of any investigational medicinal product or experimental therapy. All systemic anticancer treatments are prescribed and administered according to standard clinical practice and current institutional or national guidelines. The treating physician remains fully responsible for therapeutic decisions and management.

9.6. Compliance with study treatment

Not applicable

9.7. Concomitant Medication

Information regarding concomitant medications will be collected at baseline and updated at each relevant study visit . The following data will be recorded in the source documents and Case Report Forms (CRFs):

- name of the medication or therapy,
- indication and therapeutic class,
- route of administration,
- start and stop dates,
- dosage and frequency, and
- whether the treatment was ongoing at the time of the biopsy.

All standard-of-care treatments are permitted. No specific restrictions apply, provided that clinical conditions allow the safe performance of the on-treatment biopsy.

Medications that may interfere with coagulation (e.g., anticoagulants, antiplatelet agents, non-steroidal anti-inflammatory drugs) will be carefully evaluated prior to the biopsy procedure; temporary discontinuation may be requested in accordance with institutional safety policies to minimize bleeding risk.

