5.1. Known Potential Risks

The only additional procedure beyond routine clinical management is the on-treatment tumor biopsy, performed for translational research purposes. Potential risks are therefore limited to those commonly associated with standard biopsy procedures, as reported in the literature and routine clinical practice.

- Immediate risks: Local pain, mild bleeding, bruising, and risk of infection at the biopsy site. In rare cases, more significant complications such as hematoma or delayed wound healing may occur. These risks are minimized by performing the biopsy under sterile conditions by experienced personnel, with appropriate post-procedural monitoring.
- Long-term risks: Long-term adverse effects are not expected. Scarring at the biopsy site may persist but is usually minimal and clinically insignificant.

- Alternative procedures: No less invasive alternatives could provide the same type of tissue material necessary for the planned molecular and histopathological analyses. Peripheral blood or imaging data cannot fully replace the biological information derived from tumor tissue. Therefore, the on-treatment biopsy is justified as the only additional procedure needed to achieve the study objectives.

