10.1. Efficacy Criteria

The efficacy of the study procedure will be defined in relation to the technical and biological success of the on-treatment biopsy (.especially in terms of sample adequacy)

No clinical efficacy endpoints are foreseen.

10.2.Safety Criteria

 I.R.C.C.S. Ospedale San Raffaele	ONSET trial Protocol	Date: 10/02/2026 Version: 1.1
---	-----------------------------	----------------------------------

Safety evaluation will focus on potential adverse events (AEs) related to the biopsy procedure, since no investigational drug or device is used in this study. All AEs will be collected from the time of the biopsy until the next scheduled clinical evaluation or up to 30 days post-procedure.

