11. STUDY PROCEDURES

	Enrollment	Screening	Baseline	C1	Biopsy post CID1	C2-C8**	Surgery	Final Study Visit
Procedures		-28 (+/-3)	0 (-5)	0 (+/-2)	3-18 (+/-2)	Q3W (+/-2)	+168 (+/-56)	+190 (+15)
Informed consent	R							
Demographics	C							
Medical history	C							
Eligibility assessment	R							
Pregnancy test		C				C	C	C
Physical examination (including height and weight)	C	C	C	C		C	C	C
Vital signs	C	C	C	C		C	C	C
Performance status	C	C	C	C		C	C	C
Laboratory test (hematology and Biochemistry)		C	C	C		C	C	C
Study procedure: biopsy	C*				R		C*	
Radiologic/Imaging assessment (breast ultrasound and/or mammography and/or breast MRI)		C	C			C	C	
Adverse event assessments	C	C	C	C		C	C	C

*Done for clinical practice

**As per clinical practice

C= clinical standard of care activities; R: research activities (activities done only for the participation in the study)

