12.1 Discontinuation of study Intervention

Discontinuation from <study intervention> does not mean discontinuation from the study, and remaining study procedures should be completed as indicated by the study protocol. This may happen for a number of reasons, including but not limited to:

The occurrence of what the participant perceives as an intolerable AE.

Inability to comply with study procedures

Participant decision

Participants may choose to stop treatment and/or study assessments but may remain on study follow-up.

If a clinically significant finding is identified (including, but not limited to changes from baseline) after enrollment, the investigator or qualified designee will determine if any change in participant management is needed. Any new clinically relevant finding will be reported as an adverse event (AE).

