14.4 AE Attribution Scale

RELATIONSHIP	ATTRIBUTION	DESCRIPTION
	Unrelated	The AE is clearly NOT related to the intervention.

	ONSET trial Protocol	Date: 10/02/2026 Version: 1.1
---	-----------------------------	----------------------------------

Unrelated to investigational agent/intervention	Unlikely	The AE is doubtfully related to the intervention.
Related to investigational agent/intervention	Possible	The AE may be related to the intervention.
	Probable	The AE is likely related to the intervention.
	Definite	The AE is clearly related to the intervention.
Reference: NCI Guidelines: Adverse Event Reporting Requirements		

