14.5 Reporting procedures for AE

Given that the only study-specific procedure is an on-treatment biopsy – a well-established diagnostic technique with a well-known and limited safety profile – a risk-adapted approach will be adopted for AE reporting. Only biopsy-related adverse events (AEs) will be collected and reported in the study Case Report Form (CRF).

Routine, non-related AEs associated with anticancer treatment or underlying disease will not be systematically recorded, as they are considered part of standard clinical management and will already be documented in the patient's medical record.

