14.6 Reporting Procedures for SAE/ AESI

All Serious Adverse Events (SAEs) deemed related or possibly related to the on-treatment biopsy must be reported promptly to the Sponsor/Authorized Representative and the Ethics Committee, following institutional and regulatory timelines. Examples of biopsy-related SAEs that require immediate reporting include:

- severe bleeding requiring transfusion or surgical intervention,
- biopsy-related infection requiring hospitalization or intravenous antibiotics,
- any event leading to prolonged hospitalization, permanent damage, or death.

SAEs clearly attributable to the underlying malignancy or standard anticancer therapy (e.g., disease progression, treatment-related toxicities, hospitalization for chemotherapy complications) will not be reported as study SAEs, as they are outside the scope of this protocol.

No AESIs have been predefined for this study, as no investigational product is used and the procedure's risk profile is well established.

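### Section 9.7 lets coagulation-affecting drugs be paused for the research-only biopsy, but 10.2 starts adverse event collection at the biopsy and 5.1 does not name the risk of a pause (minor)

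*Protocol*

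**What the plan says.** **The pause.** Section 9.7 names anticoagulants, antiplatelet agents and NSAIDs as drugs to be assessed before the biopsy and adds that "temporary discontinuation may be requested in accordance with institutional safety policies to minimize bleeding risk". The section 11 schedule codes this biopsy R, meaning it is done only for the study.

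**The stated risks.** Section 5.1 says: "Potential risks are therefore limited to those commonly associated with standard biopsy procedures". Its list is local: pain, bleeding, bruising, infection, rarely haematoma or slow healing, and scarring in the long term. Interrupting a drug is not on it.

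**AE collection.** Section 10.2 says: "All AEs will be collected from the time of the biopsy until the next scheduled clinical evaluation or up to 30 days post-procedure". Section 14.5 says: "Only biopsy-related adverse events (AEs) will be collected and reported in the study Case Report Form (CRF". It does not say whether harm from a pause requested for the biopsy counts as biopsy-related.

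**Serious events.** Section 14.6 covers serious events "deemed related or possibly related to the on-treatment biopsy must be reported promptly" and sets no start date. Section 14.4 describes the category Possible as "The AE may be related to the intervention" and places it on the related side.

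**The concern.** A pause requested for this biopsy is driven by the study, because without the study there would be no biopsy at that time. Its purpose is to lower bleeding risk, so it must start before the procedure. The AE window starts later than that, and the risk statement leaves the pause out. The protocol therefore describes a measure against one harm (bleeding) without naming the harm that the measure itself can bring.

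At stake is the completeness of the safety record for the one study-specific procedure. Section 10.2 makes biopsy-related events the focus of the safety evaluation. No analysis of gene expression, cell clustering or pathological response depends on this.

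**Working it through.** No figure in the protocol can be reproduced here. The check is to set the rules side by side for one event: a patient stops a drug at time P because the study biopsy is planned for time B, and something happens between P and B.

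1. **Timing.** To reduce bleeding at the biopsy, P must precede B. The section 10.2 window opens at B, so it covers 0 days of the interval from P to B. The protocol gives no length for a pause, so the number of uncovered days cannot be stated. Anything that appears at or after B falls inside the window.

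2. **Coverage of an event between P and B.**
   - Section 10.2: not covered.
   - Section 14.5: covered only if classed as biopsy-related, and the text is silent on that.
   - Sections 14.4 and 14.6: covered if the event is serious and judged at least possibly related to the biopsy.
   - Section 9.7: the medication record holds stop dates and whether the drug was being taken at the biopsy. That documents the pause but not harm from it, and the list has no field for why the drug was stopped.
   - Section 11 schedule: the row "Adverse event assessments" is coded C (clinical care) in 7 of 8 columns (Enrollment, Screening, Baseline, C1, C2-C8, Surgery, Final Study Visit). It is blank in the biopsy column and coded R in none. An event would probably be seen in routine care, but the schedule does not bring it into the study record.

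3. **Attribution.** The biopsy is scheduled on days 3–18 after C1 with a tolerance of 2 days either way: 3 − 2 = day 1 to 18 + 2 = day 20. The first treatment cycle is thus always recent at the biopsy. Section 14.6 leaves out serious events clearly due to the cancer or its treatment, so an event during a pause could be put down to either of these.

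4. **Number affected.** Planned enrolment is 20 + 35 = 55. The protocol gives no frequency for use of these drugs, for pauses or for resulting events. Section 9.7 makes the pause optional, and exclusion criterion 9 removes patients in whom the biopsy is contraindicated. The number could be 0 of 55, and no useful upper figure follows from the text.

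5. **Endpoints.** Section 6 lists no safety endpoint, so none is affected.

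**The case against.** The strongest reply is that the protocol already catches what matters. Serious events possibly related to the biopsy are reportable with no start date, and section 14.6 includes among its examples events leading to prolonged hospitalisation, lasting damage or death. Section 14.5 is silent, not exclusionary: what it sets aside are unrelated events tied to cancer treatment or the disease, and harm from a pause made for the biopsy is neither. The pause is optional and follows institutional policy. Drug management around a biopsy can also be read as part of the ordinary practice that section 5.1 invokes.

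Most of this stands and sets the size of the point. It does not move the start of the section 10.2 window, and section 5.1 still limits the risks without listing this one.

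A reader might infer more than the text supports:
- **Serious harm would go unreported.** Sections 14.4 and 14.6 say otherwise, provided relatedness is judged correctly.
- **Participants are not told of the risk.** The consent pages and the institutional policy are not available, so an omission from section 5.1 does not show this.
- **Sites would report differently.** The study has a single centre.
- **Other wording conflicts add weight.** Section 12.1 would have any new clinically relevant finding after enrolment reported as an AE, which sits badly with section 14.5. Section 14 denies any intervention beyond routine care, although sections 5 and 9 acknowledge the research biopsy. Both deserve correction for consistency, but neither arises from the drug pause and neither supports this point.

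**Conclusion.** The point holds as a minor defect in two places: the start of the AE window in section 10.2 and the risk statement in section 5.1. A related silence in section 14.5 should be settled at the same time. The uncovered events are mainly non-serious ones, or serious ones wrongly attributed to cancer or chemotherapy, that occur during a pause before the biopsy.

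This rests on two readings: that a pause meant to lower bleeding starts before the biopsy, and that a pause requested for a research-only biopsy is a consequence of the study. Both follow closely from sections 9.7 and 11. How often it would matter is unknown and may be never.

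**What to change.** - **Section 10.2:** start AE collection at the earlier of the biopsy or any medication interruption requested for it.
- **Section 14.5:** state that events attributable to such an interruption count as biopsy-related.
- **Section 5.1:** add the risk of interrupting these drugs.

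Decisions on which drugs to stop, and for how long, stay with institutional policy.

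The cost is a few sentences and no extra visit. The risk statement becomes slightly less favourable, and a few more events may be reported. One small addition to the record is needed: a reason such as stopped for study biopsy, noted beside the stop date that section 9.7 already collects, so that these interruptions can be told apart from others.

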9.8 Other Interventions

Not Applicable

10. EFFICACY AND SAFETY CRITERIA

The study does not evaluate therapeutic efficacy in terms of clinical outcomes, since systemic treatments follow standard-of-care protocols. The objective of this project is exploratory and translational in nature.

10.1. Efficacy Criteria

The efficacy of the study procedure will be defined in relation to the technical and biological success of the on-treatment biopsy (.especially in terms of sample adequacy)

No clinical efficacy endpoints are foreseen.

10.2.Safety Criteria

 I.R.C.C.S. Ospedale San Raffaele	ONSET trial Protocol	Date: 10/02/2026 Version: 1.1
---	-----------------------------	----------------------------------

Safety evaluation will focus on potential adverse events (AEs) related to the biopsy procedure, since no investigational drug or device is used in this study. All AEs will be collected from the time of the biopsy until the next scheduled clinical evaluation or up to 30 days post-procedure.

11. STUDY PROCEDURES

	Enrollment	Screening	Baseline	C1	Biopsy post CID1	C2-C8**	Surgery	Final Study Visit
Procedures		-28 (+/-3)	0 (-5)	0 (+/-2)	3-18 (+/-2)	Q3W (+/-2)	+168 (+/-56)	+190 (+15)
Informed consent	R							
Demographics	C							
Medical history	C							
Eligibility assessment	R							
Pregnancy test		C				C	C	C
Physical examination (including height and weight)	C	C	C	C		C	C	C
Vital signs	C	C	C	C		C	C	C
Performance status	C	C	C	C		C	C	C
Laboratory test (hematology and Biochemistry)		C	C	C		C	C	C
Study procedure: biopsy	C*				R		C*	
Radiologic/Imaging assessment (breast ultrasound and/or mammography and/or breast MRI)		C	C			C	C	
Adverse event assessments	C	C	C	C		C	C	C

*Done for clinical practice

**As per clinical practice

C= clinical standard of care activities; R: research activities (activities done only for the participation in the study)

11.1. Informed Consent

All participants will provide written informed consent prior to any study-specific procedures or data collection, in compliance with ICH GCP and applicable regulations. The investigator or a designated team member will explain the study objectives, procedures, potential risks and benefits, and participants' rights in terms they can understand, answering any questions. Participants will have time to review the consent form, discuss it with family or surrogates, and consider their decision. Participation is voluntary, and participants may withdraw at any time without affecting their medical care. Written consent, including the date, will be documented in the source records, and a copy of the signed form will be given to the participant.

11.2. Subject Recruitment and Screening

Participants will be identified through outpatient clinics at Ospedale San Raffaele and approached by the study team. Screening will include verification of inclusion/exclusion criteria, review of medical history, concomitant medications, physical examination, performance status (ECOG), and relevant laboratory or diagnostic tests. Recruitment is expected to be completed over approximately 36 months, with all participants enrolled at the single study site.

11.3. Subject Identification

Participants are considered enrolled once informed consent is signed by the patient or their legal representative. Each participant will receive a unique study code (e.g., ON_TN_XX; where ON_TN is the abbreviation of the Protocol Code, XX is the progressive subject number in increasing order starting from 01) for tracking, and a confidential list linking codes to identities will be maintained at the study site.

11.4 Randomization and Blinding

Not applicable

11.5 Baseline Assessments

At baseline, all participants will undergo assessments necessary to meet the study objectives and endpoints. These include verification of eligibility criteria, medical history, physical examination, performance status (ECOG), laboratory tests, imaging as indicated, and collection of tumor tissue for molecular and immune profiling. Baseline biopsies will be obtained prior to the initiation of neoadjuvant therapy, as per standard care.

11.6 Visits and Follow Up

Participants will be evaluated at defined study visits:

Visit 0 (Enrollment): Screening, informed consent, eligibility confirmation, medical history, physical examination

Neoadjuvant Phase: Clinical evaluation, on-treatment tumor biopsy for molecular analyses after first cycle of standard therapy

Surgery: Clinical assessment

Final study visit (20–45 days after surgery): As per standard clinical practice, participants will be followed for safety and outcome assessments. Clinical evaluation, collection of surgical specimen, evaluation of pCR.

11.7 Definition of End of Study

According to the study design, the end of the study is defined as the date on which the last patient completes the last visit.

11.8 Premature termination or suspension of a study

This study may be temporarily suspended or prematurely terminated by the Principal Investigator or the authorized Sponsor representative if there is reasonable cause. Possible reasons include insufficient compliance with protocol requirements, incomplete or unevaluable data, determination that the primary endpoint has been met, or futility of the study. In such cases, written notification documenting the reason will be provided to study participants, the Ethics Committee, and relevant regulatory authorities

12 DISCONTINUATION AND WITHDRAWAL

Participants are free to withdraw from the study at any time, for any reason, without any impact on their medical care.

12.1 Discontinuation of study Intervention

Discontinuation from <study intervention> does not mean discontinuation from the study, and remaining study procedures should be completed as indicated by the study protocol. This may happen for a number of reasons, including but not limited to:

The occurrence of what the participant perceives as an intolerable AE.

Inability to comply with study procedures

Participant decision

Participants may choose to stop treatment and/or study assessments but may remain on study follow-up.

If a clinically significant finding is identified (including, but not limited to changes from baseline) after enrollment, the investigator or qualified designee will determine if any change in participant management is needed. Any new clinically relevant finding will be reported as an adverse event (AE).

13 SAMPLE HANDLING

All samples collected in this study consist exclusively of tumor tissue and are obtained as part of routine clinical practice (baseline tumor biopsy or surgical sample) or as per protocol (on treatment biopsy). All tissue samples used for research analyses, including molecular and immune profiling, are fully integrated into the participants' clinical management. After the routine analysis of the Pathologic Unit, only the necessary tumor material from biopsies for the experiment will be transferred to CRB for temporary storage and will be completely used for analysis of the study by SR-tiget. No residual material is expected to remain. In the event of any leftovers, it will be destroyed by our collaborator.

The SR-TIGET will perform single-cell RNA-seq of TNBC specimens obtained on pre-treatment, on-treatment and after-treatment (in cases with RD) from patients receiving neoadjuvant chemo-immunotherapy at OSR.

The laboratory of [name], in Cambridge UK will characterize the comprehensive tumor/immune molecular landscape dynamic by analyzing scRNA-seq and integrating this information with those already available and in particular with spatially resolved single cell analysis. They will not receive any biological material from tumor biopsies, but only raw experimental data obtained by single-cell RNA-seq.

14 PATIENT SAFETY

All procedures performed in this study are part of standard clinical practice. No additional interventions or experimental treatments are being introduced beyond routine care; therefore, no additional safety risks are anticipated for study participants.

